6.7.2 Use of Safety results in future labeling

A summary of SAE, UADE and DRAE will be included in future labelling of the NBT device.

6.8 ASSESSMENT OF BLINDING SUCCESS

Subject blinding Success

The patients will be asked at the end of the baseline visit (Visit 2), at the end of the first treatment visit (Visit 3), at the end of the last treatment visit (Visit 20 and at the 6 month followup visit (Visit 24) whether they think they were in the active group or in the sham group. The data will be summarized with frequency and percentage by actual treatment received. Chisquare test will be used for this assessment of subject blinding success.

Outcome Assessment Therapist Blinding Success

Outcome assessment therapists will be asked at the first follow-up visit (Visit 21) and at the 6 month outcome assessment visit (Visit 24) whether they think the subject was in the active rTMS group or in the sham rTMS group or they didn't know. The data will summarized with frequency and percentage by treatment group received. Chi-square test will used for assessment of outcome assessment therapist blinding success.

In addition, the therapists will be asked if the study staff revealed group randomization and if the subject told them what group they believed they were in. The data will be summarized for those therapists who don't know which group the subject was in and those who think the subject was in either the active or sham rTMS group separately. The data will used for background information to explain the results of assessment of therapist blinding success.

7.0 Monitoring and quality assurance

INDEPENDENT MONITORING OF SOURCE DATA AND SAFETY

The data will be collected by staff members (PI, co-investigators and study staff) familiar with the protocol and the TMS technology. The care, safety, and comfort of the subjects will be under the supervision of a physician and therapist at each trial site).

Clinical monitoring

The study sponsor will be responsible for Clinical Monitoring of the study. The Clinical Monitor's responsibilities include maintaining regular contact with the clinical site through telephone contact and on-site visits, to ensure that:

- the trial is conducted according to protocol;
- the Investigational Plan is followed;

- study staff is trained and capable of performing the tasks required from them in a uniform manner at each trial site. The central site (Rehabilitation Institute of Chicago) will provide training for all assessors and therapists. At the beginning of the study and every 6 months during the study all assessors will be trained, certified and/or re-certified for their role. Additional training will be provided to study staff who do not pass the review. Staff members will only be permitted to perform study duties if they have successfully passed their most recent evaluation.

- complete, timely, and accurate data are recorded and submitted;
- problems with inconsistent or incomplete data are addressed;
- complications and unanticipated adverse effects are reported to the IRB and Sponsor;
- the site facilities continue to be adequate to meet the requirements of the study.

The Clinical Monitor will initiate the Study during an on-site visit and will continue to perform on-site monitoring visits as frequently as deemed necessary. The first monitoring visit will usually be made as soon as possible after enrollment has been initiated. At this visit and all monitoring visits, the Clinical Monitor will compare the data entered onto the CRF's with the hospital or clinic records (source documentation). At a minimum, source documentation must be available to substantiate proper informed consent procedures, adherence to protocol procedures, adequate reporting and follow-up of AEs. Findings from the review of CRFs and source documents during a monitoring visit will be discussed with the PI. Completed pages of the CRFs will be collected for evaluation at each visit. The dates of the monitoring visit will be recorded in a Log to be kept at the clinical site. During monitoring visits, the Sponsor expects that the study coordinator and the PI will be available (as needed), the source documentation will be available, and a suitable environment will be provided for review of Study related documents.

Independent Data and Safety Monitoring Board

The study will be performed under the supervision of an Independent Data Monitoring Board (DSMB) that will consist of clinician who are not Investigator(s) in the study, and one independent statistician.

Details of the DSMB composition and operational activities will be described in detail in a separate DSMB charter.

Briefly, the DSMB responsibilities are to:

- evaluate the progress of the trial, including assessments of data quality and timeliness, participant recruitment, accrual and retention, participant risk versus benefit, performance of trial sites, and other factors that can affect study outcome;
- consider factors external to the study when relevant information becomes available, such as scientific or therapeutic developments that may have an impact on the safety of the participants or the ethics of the trial;
- protect the safety of the study participants;
- report on the safety and progress of the trial;
- make recommendations to the Sponsor, the PI, and, if required, to the Food and Drug Administration (FDA) and the Institutional Review Board (IRB) concerning continuation, termination or other modifications of the trial based on the observed beneficial or adverse effects of the treatment under study;

•

- ensure the confidentiality of the trial data and the results of monitoring; and,
- assist Sponsor by commenting on any problems with study conduct, enrollment, and sample size and/or data collection.

All subjects will be monitored by a member of study staff during the study visits. All cases performed during a calendar month will be reviewed at the end of that month to monitor for any potential adverse effects from the subjects' participation in the study.

ADVERSE EVENT REPORTING GUIDELINE

Serious_adverse events will be reported to the IRB and the sponsor verbally within 24 hours, followed by a full written report within 10 working days. All other adverse events will be summarized in the progress report at Continuing Review by IRB and evaluated by DSMB. All adverse events will be assessed for their relationship to the study device or procedure by DSMB.

Throughout the study, adverse events and concomitant medications will be monitored and recorded. All Serious Adverse Events will be captured and assessed. All Serious Adverse Events will be reported as event and patient based count.

ADVERSE EVENT

An adverse event (AE) is any undesirable clinical experience (any sign, symptom, illness, abnormal laboratory value or other medical event) that occurs in a subject (or an event that worsens during the course of the study) and that could possibly be associated with the investigational product, procedure or medications required by this protocol. An adverse event may result from a device failure if an undesirable clinical event occurs. In this study, subjects should be encouraged to report AEs spontaneously.

Adverse event information will be collected throughout the study. Data collection will include event type, date of onset severity relationship to the procedure and investigational device, and event resolution, if any, at the conclusion of the study. All events will be followed for the duration of the study until they are resolved or their status at study conclusion is explained.

Serious Adverse Event

Each study investigator must decide whether an adverse event meets the definition of a "serious" adverse event. The regulatory definition of a serious adverse event (SAE) is an event that is fatal or life-threatening, results in persistent or significant disability, requires intervention to prevent permanent impairment, results in hospitalization (or prolongation of a hospitalization) or results in congenital anomaly or malignancy.

Any serious adverse event or subject death occurring during the study follow-up period must be reported within one working day after the investigator learns of the event.

Device Failure, Malfunctions and Near Incidents

Investigators are instructed to report all possible device failures, malfunctions or near incidents observed during the course of the trial. These incidents will be documented in the case report form provided as follows:

Device Failure: A device failure has occurred when the device is used in compliance with the study protocol, but does not perform as described in device manual and also negatively impacts treatment of the study subject.

Device Malfunction: A device malfunction occurs when an unexpected change to the device that is contradictory to the device manual is observed, which may or may not affect device performance.

Device Misuse: Any use of the investigational device by an investigator that is contradictory to the application described in the study protocol will be categorized as device misuse.

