6.7 SAFETY ANALYSES

The Safety Population will be used for all analysis, summaries, and listings of safety data.

Adverse Events

All reported terms (investigator descriptions) for AEs will be coded using the most recent version of the Medical Dictionary for Regulatory Activities (MedDRA v16.0) and summarized with frequencies and percentages by treatment group, system organ classification, and preferred term.

Note that subjects experiencing AEs are counted at most one time per preferred term and at most one time per system organ class, at the highest recorded severity and causality. Events without recorded relationship or causality are summarized as severe or definitely related.

The number and percentage of subjects in the following categories will be summarized by group and overall: subjects with AE, TEAE, SAE, TESAE, UADE, DRAE, TEAE resulting in study discontinuation, and deaths.

The following tables will also be presented:

- All TEAEs
- SAEs and TESAEs
- TEAEs by severity
- TEAEs leading to premature discontinuation of study treatment.

Separate data	listings	W1II	be	presented	for	all	AEs	and	SAES.
---------------	----------	------	----	-----------	-----	-----	-----	-----	-------

Unanticipated Adverse Device Events (UADE)

A UADE is defined as any AE that is definitely related to the study device. All UADEs will be summarized by System Organ Class and Preferred Term. A listing of UADEs will also be provided.

Device-Related Adverse Events (DRAE)

A DRAE is defined as any AE that is possibly, probably, or definitely related to the study device. All DRAEs will be summarized by System Organ Class and Preferred Term. A listing of DRAEs will also be provided.

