6.7.1 Primary Safety Analysis

The use of study treatment will be considered safe if the proportion of SAEs in the active rTMS group is not statistically significantly higher than that in the sham group. Number of subjects with SAEs and TESAEs will be summarized by group and compared using a Chi Square test.

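### The AE definition makes possible association with the study a condition of being an AE, which conflicts with the all-SAE comparison and could leave serious events unrecorded

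*Combined protocol and SAP*

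**What the plan says.** Section 7.0 (Adverse Event) describes an AE as an undesirable clinical experience that arises or worsens in a subject, and then adds a second condition, that it be one "that could possibly be associated with the investigational product, procedure or medications required by this protocol".

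The later steps refer back to that term:

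- Section 7.0, Serious Adverse Event: "Each study investigator must decide whether an adverse event meets the definition of a" serious one. The SAE definition itself has no causal element. An SAE "is an event that is fatal or life-threatening, results in persistent or significant disability", and the list continues with other outcomes.
- Section 7.0, Adverse event reporting guideline: "All adverse events will be assessed for their relationship to the study device or procedure by DSMB". The same part says that all SAEs will be captured.
- Section 7.0, on what is recorded: "Data collection will include event type, date of onset severity relationship to the procedure and investigational device".
- Section 6.7: "A DRAE is defined as any AE that is possibly, probably, or definitely related to the study device".
- Section 6.7.1: "The use of study treatment will be considered safe if the proportion of SAEs in the active rTMS group is not statistically significantly higher" than in the sham group, tested by chi-square on the number of subjects with SAEs and TESAEs. Section 6.7.2 puts an SAE summary into future labelling.

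Section 3.2 says that all SAEs will be recorded and compared between groups. Section 7.0 also requires any SAE or death during follow-up to be reported within one working day. No sentence says that AEs or SAEs are recorded whatever their cause.

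**The concern.** A randomised comparison of all-cause SAEs needs no judgement about what caused each event. That is its main protection. A definition that asks about association before an event is counted gives the protection up, and it does so before the DSMB sees anything.

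The population makes this practical. Section 2.2 notes that many candidates have cardiovascular disease and hypertension. Follow-up runs to 6 months after the last session, and sections 5.2 and 6.3 anticipate new strokes. These are events that someone could regard as unassociated with stimulation given months before. Five sites could also read the definition differently, which would make SAE ascertainment uneven.

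What is at stake is the safety conclusion in section 6.7.1, the labelling summary in 6.7.2, and the interpretability of the AE and DRAE tables.

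**Working it through.** **Tracing the definitions.** The plan gives no figure on this point to reproduce, so the first check is to set the texts side by side.

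1. The AE definition joins its two parts with a conjunction, so possible association is a condition of entry and not a comment on it.
2. Seriousness is decided for an adverse event. On this reading SAEs are a subset of AEs, and an event that fails step 1 never reaches the seriousness decision.
3. The DSMB assesses the relationship of adverse events. An event that fails step 1 is not put to it under this rule.
4. The chi-square test in 6.7.1 counts subjects with SAEs, so it inherits whatever steps 1 and 2 leave out.
5. Other texts point the opposite way. The SAE criteria name an event and look only at outcome. Section 3.2 and the capture sentence in 7.0 cover all SAEs. The relationship field and the DRAE definition treat relatedness as an attribute graded after an event has been recorded.

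Steps 1 to 4 and step 5 cannot both be followed for a serious event thought unassociated. The exception is death, which is reportable in its own right.

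**How sensitive is the safety test?** Inputs: about 30 per arm (section 5.2.3), two-sided 0.05 (section 6.5), uncorrected chi-square. I assume that the safety population is 30 per arm. With a active and c sham subjects having SAEs and m = a + c,

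chi-square = 60(a − c)² / [m(60 − m)], critical value 3.84.

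| Active v sham | Calculation | Chi-square | Significant? |
|---|---|---|---|
| 3 v 0 | 60×9 / (3×57) | 3.16 (p = 0.076) | no |
| 4 v 0 | 60×16 / (4×56) | 4.29 (p = 0.038) | yes |
| 5 v 0 | 60×25 / (5×55) | 5.45 | yes |
| 5 v 1 | 60×16 / (6×54) | 2.96 | no |
| 6 v 1 | 60×25 / (7×53) | 4.04 | yes |

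Losing one active subject from 4 v 0 removes significance. Losing the one sham subject from 5 v 1 creates it. Dropped events can therefore move the conclusion either way.

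**Effect on power.** The documents give no SAE rates. As an illustration only, assume 30% active and 10% sham, with 10% in each arm being background.

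Power = Φ{[(p₁ − p₂) − 1.96√(2p̄(1 − p̄)/30)] / √[(p₁(1 − p₁) + p₂(1 − p₂))/30]}

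- All SAEs counted (30% v 10%): (0.20 − 1.96×0.1033)/0.1000 = −0.02, power 49%.
- Half of all SAEs dropped in both arms (15% v 5%): (0.10 − 1.96×0.0775)/0.0764 = −0.68, power 25%. With three quarters dropped (7.5% v 2.5%), 14%.
- Half of the background SAEs only dropped (25% v 5%): (0.20 − 1.96×0.0922)/0.0885 = 0.22, power 59%. With three quarters dropped (22.5% v 2.5%), 66%.

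Indiscriminate omission lowers power, and perfectly accurate omission raises it. The direction depends on how good the judgement of association is, and the documents say nothing about that.

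**The case against.** The strongest reply is that the AE sentence should be read with its neighbours. The SAE definition is a separate, outcome-based one, all SAEs are to be captured, and deaths are reported regardless. A careful site might well report every serious event. This stands in part: loss of SAEs is a possible consequence of the wording, not a certain one. It does not remove the conflict, because the seriousness decision is still framed as applying to adverse events.

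The reply can add that the threshold is low and that other procedures reduce the risk. Section 5.2.4 has new medical problems reviewed at each treatment visit, section 7.0 has the monitor compare forms with source records and all cases reviewed monthly, and section 6.7 counts events lacking a recorded relationship as definitely related. These help, but none tells a site to record an event it thinks unassociated, and the 6.7 rule acts only on events already recorded. The case report form, the DSMB charter and the separate statistical analysis plan named in section 6.1 may hold further capture rules. They are not available here.

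On size, the reply is right. If 5 to 10% of 60 patients had an SAE (an assumption; 3 to 6 patients), significance would require at least four affected patients, all in the active arm. Losing one or two would seldom change the formal conclusion.

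A reader might infer three stronger things that the documents do not support:

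- That site staff screen for causality. No sentence assigns this judgement to anyone. It is only an inference from the investigator's role.
- That AEs and DRAEs become nearly the same set. The AE clause also covers procedures and protocol-required medications, whereas a DRAE concerns the device alone. An event linked only to the therapy sessions would be an AE and not a DRAE.
- That the omission favours the active arm. Under section 5.1.1 only the person responsible for randomization and those giving rTMS know the allocation, so nothing shows that omission would differ by arm.

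**Conclusion.** The concern holds as an inconsistency in a stated rule. Followed literally, the AE definition can keep a serious non-fatal event that is thought unassociated out of the AE and SAE records, and so out of the comparison in section 6.7.1. It also contradicts the outcome-only SAE criteria, the promise to capture all SAEs, the separate relationship field and the graded DRAE definition.

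The conclusion rests on reading the association clause as a condition and SAEs as drawn from AEs. Both follow from the wording, but the second is open to dispute. Who would apply the condition and how many events it would remove are not stated. The effect on the test has no fixed direction, and every rate used above is an assumption. The point deserves correction because events never recorded cannot reliably be recovered at analysis, not because a bias of known size has been shown.

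**What to change.** In section 7.0, delete the association clause from the AE definition and state that all AEs and SAEs after enrolment are recorded regardless of causality. Keep relationship only where the plan already has it, in the data field and the DSMB assessment. No new causality field is needed. Then check that the AE, SAE and death-reporting text in 7.0, the DRAE definition in 6.7 and the comparison in 6.7.1 use the terms in the same sense.

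The cost is a wording change and a modest increase in AE forms. It should be made before data collection. If enrolment has begun, source records would need checking for events left out, and recovery may be incomplete.

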Appendix A NBT PROCEDURES

GENERAL

For the navigated TMS session with NBT, the subject will undergo the MRI to head registration and Motor Threshold and TMS procedures. Each TMS imaging session will begin with aligning the MRI images to the subject's head via the MRI to head co-registration. Subjects will then undergo TMS mapping of the hand motor areas as set out below to localize optimal the motor representation area of hand muscles including the muscle of interest, m.EDC.

ELECTROMYOGRAPHY

EMG leads must be connected to m.EDC and m.APB to facilitate accurate mapping of the m.EDC motor representation areas:

- 1. Abductor Pollicis Brevis (APB)
- 2. Extensor Digitorum Communis (EDC)

NOTE: The target muscle(s) should be at rest at all times. Monitor involuntary muscle activity at all times during the examination.

MRI TO HEAD CO-REGISTRATION

Using the nasion and the crus of helix of the ears, landmarks that are visible on both the subject's MRI and the head, the 3D -locations of landmark are measured using a digitizing pen with an optical tracking system. This registration will allow real time monitoring of the coil position without restraining the subjects head during the TMS experiment. The optical tracking system uses a camera to measure the 3D -location of infrared reflectors attached to the coil and subject's head.

BASELINE, TREATMENT VISITS

The motor mapping of the healthy hemisphere will be done during the baseline visit and this location will be utilized in determining the motor threshold and therapy intensity during each treatment visit when rTMS is administered. Motor mapping of the lesioned hemisphere will not be performed. The following list illustrates which procedures are done during the first and subsequent visits. The details of the steps are described in the following sections.

1) Healthy hemisphere

- a) Baseline visit
 - i) Hand area motor mapping
 - (1) Initial motor mapping
 - (2) Initial motor threshold
 - (3) Refined mapping
 - ii) Therapy dose determination
 - (1) Refined motor threshold
 - iii) Offline analysis
- b) Following visits
 - i) Therapy dose determination
 - (1) Refined motor threshold

- ii) Therapy delivery
- iii) rTMS stimulation
- iv) Offline analysis

HEALTHY HEMISPHERE

HAND AREA MOTOR MAPPING

Localization of the cortical representation area for m.EDC at rest is described here.

Attach mapping coil (Nexstim Focal Coil)

Mapping of the motor cortical representation areas and determination of motor thresholds will be done using the Nexstim Focal Coil. Attach the coil to the system if not already connected.

Identifying the rough location of hand motor area

This identification of the rough location of hand motor area is used in determination of the initial motor threshold and as a reference for the actual motor mapping.

- 1) Identify the hand knob at primary motor cortex, if possible.
 - a) Peel the 3D head to a depth where the gyral patterns of neuroanatomy are clearly visible (approximately 20-25 mm)
 - b) For reference utilized during mapping place a stimulation target on the motor cortex. The position of the marker is on the medial end of the so called "motor knob" on the central sulcus.
- 2) Set initial stimulation intensity
 - a) Adjust stimulator output so that the software displays stimulation intensity between 80 and 100 V/m (at 25 mm peeling depth).
 - b) Give a preparing stimulus pulse on the marker and check the response of the target muscle m.EDC
 - c) Give two stimuli are on the target and check m.EDC response latencies (normal 15-25ms) and amplitudes.
 - i) IF YOU GET EMG RESPONSE >500uV: Lower the stimulation intensity 1-2 % of stimulator output and repeat stimulation until the m.EDC peak-to-peak response is in the range of 100-500uV.
 - ii) **IF YOU GET EMG RESPONSE <100uV**: Increase the intensity of stimulus until the m.EDC amplitude is 100-500uV.
- 3) Using the intensity defined in the previous step, continue stimulation by following the central sulcus towards the central fissure so that the stimulus orientation is always perpendicular to the central sulcus and direction frontal. Stimulation is ended when there is no response. This is most likely to happen about 2 cm from the marker. **NOTE:** Make sure that you stimulate also directly over the precentral gyrus. Return to the marker and continue stimulation by following the central sulcus towards the Sylvian fissure so that the stimulation direction is always perpendicular to the central sulcus. Expand the stimulated area until MEP's disappear.
- 4) Select the largest m.EDC response and set is as Repeat Stimulus.

- 5) Testing coil orientations:
 - a) The first stimulus is given on the repeat stimulus target. This is the zero degree position. Check the EMG response amplitude which is now the reference. Turn off location controlled stimulation. Using the aiming tool to repeat stimulus on the marker, the stimulation on the marker is continued so that after each stimulus the coil is turned 20 degrees left. The m.EDC response amplitude (μ V) is checked after each given stimulus. The stimulation is terminated when the response is less than 100 μ V.
 - b) Return to the original orientation on the marker and continue stimulation on the marker so that after every stimulus the coil is turned 20 degrees right. After every stimulus the response amplitude (μ V) is checked. Stimulation is terminated when the response is less than 100 μ V.
 - c) The coil orientation giving the best motor response is selected for defining the motor threshold.

Initial motor threshold measurement for defining intensity for motor mapping: The motor threshold (MT) is defined as the lowest stimulation intensity producing a response in the target muscle (m.Extensor Digitorum Communis, m.EDC) at least in 50% of trials. The presumption is that the motor threshold varies due to the functional state of the brain which may be altered by lesions or medications.

- 1) Start the MT determination tool from the stimulus defined in the previous step.
- Stimulate guided by the Aiming Tool as many times as suggested by the software, leaving 3-5 seconds between each stimulus.
- 3) In the end of the iteration, the software displays the patient's motor threshold value as a percentage of the maximum stimulator output.

Mapping of hand motor area and localization of m.EDC hotspot

Mapping of the cortical representation area of the hand area is now repeated using a stimulator intensity that generates $\sim 100-300\mu V$ MEPs repeatably at the location where resting motor threshold is determined. Typically this is 110% of the resting motor threshold.

The overall goal is to find a stimulation location, on or near the motor strip, that elicits the largest amplitude EDC MEP during mapping with other relatively large EDC MEPs elicited at the same location or at nearby locations.

- 1) Set the stimulator output to 110% of the motor threshold defined previously
- 2) Once the stimulation intensity is determined, the rMT determining location should be set as the active stimulation target to overlay a stimulation Grid on cortex.

CONFIDENTIAL

- 3) Using the Grid to systematically cover the area to be studied, stimulate along central sulcus, precentral gyrus, postcentral sulcus and precentral sulcus with 2-3 mm spacing of stimuli while keeping the electric field orientation perpendicular to the sulcus. Mapping should proceed with 3 stimuli per grid location, delivered with 3-4s between pulses, until stimulation at locations around the "rim" or outer edge of the map do not produce reproducible MEPs (=at least 2/3 stimuli to location do not elicit a MEP >50 μ V).
- 4) Expand the stimulated area as long as reproducible motor responses emerge.
- 5) Identify the location giving rise to the largest m.EDC EMG response the target for rTMS
- 5.1 Rank the EDC MEPs by amplitude
- 5.2 Select the MEP with highest amplitude that fills as many of the following criteria as possible
- 5.2.1 Background EMG was quiet during this stimulation
- 5.2.2 The location is on or near the motor strip
- 5.2.3 The other two MEPs generated at this location are also large
- 5.2.4 There is also a clear resting MEP in APB
- 5.2.5 The adjacent locations also have strong, repeatable MEPs.
- 5.3 NOTE: The location chosen may not be the absolute highest amplitude MEP from the mapping. We are trying to find a location that represents the strong center of activation for hand and finger muscles, shown by large repeatable MEPs. We want to avoid selecting an isolated activation center for EDC far from M1, or one that represents a transient high fluctuation in cortical excitability.
- 6) Test coil orientations in this location as done in initial mapping and select the best motor response is for defining the refined motor threshold

The location defined in the refined mapping including coil orientation testing is considered the hotspot of m.EDC and will be used as the target location for subsequent MT determinations and delivering 1 Hz rTMS therapy.

THERAPY DELIVERY

For rTMS delivery the best coil orientation giving rise to the largest m.EDC response from refined mapping will be used as the coil orientation during rTMS delivery. The rTMS delivery will be performed at 110% of the motor threshold determined at this location in the previous step.

A single 1Hz train consisting of 900 stimuli will be delivered to the hotspot of motor representation area of m.EDC established at the baseline visit.. Active or sham rTMS will be delivered utilizing an active or sham coil, respectively.

Attach the TMS coil appropriate for the subject's randomization group (Nexstim Trial Coil)

Motor threshold measurement for defining intensity for rTMS therapy.

The location defined in the refined mapping including coil orientation testing is considered the hotspot of m.EDC and will be used as the target location for subsequent MT determinations and delivering 1 Hz rTMS therapy.

- 1) Start the MT determination tool from the stimulus defined in the previous step.
- Stimulate guided by the Aiming Tool as many times as suggested by the software, leaving 3-5 seconds between each stimulus. For subjects randomized to receive sham stimulation, alternatively accept and reject the results suggested by the NBT software.
- 3) In the end of the iteration, the software displays the patient's motor threshold value as a percentage of the maximum stimulator output.

RTMS stimulation

- 1) Select the stimulus corresponding to the largest m.EDC response from refined motor mapping (same stimulus as used as reference during refined MT determination) and set it as Repeat Stimulus
- 2) Position therapy coil using coil positioning holder to location guided by Aiming Tool
- 3) Select rTMS sequence containing 900 stimuli at 1 Hz (15 minute duration)
- 4) Check that the intensity corresponds to 110 % of the refined m.EDC MT defined in previous step
- 5) Start rTMS sequence and monitor coil position

OFF-LINE ANALYSIS

- 1) From details of the therapy rTMS sequence review statistics for accuracy of pulses in relation to the reference pulse / first pulse of sequence, i.e. how well the coil stayed in place during the sequence run.
- 2) From motor mapping, identify optimal m.APB and EDC locations (the stimulus location evoking the largest EMG responses, respectively).
- 3) Define coil coordinates, coordinates on the chosen stimulation surface (3D-MR image), and coordinates at fixed depth (25 mm from the scalp surface). Review MEP traces and correct the amplitudes and latencies if needed.
- 4) Capture all stimuli eliciting muscle responses with normal latencies and greater than or equal to 50 μ V in relaxed muscles.

- 5) Make an analysis file to NBT for further studies.
- 6) Establish a map of motor cortical locations from the analysis file by using the NBT analysis table and its visualization features.

